16.4.1. ORTHOSTATIC EFFECTS

Orthostatic hypotension is defined as a decrease of \geq 20 mmHg in systolic blood pressure or \geq 10 mmHg in diastolic blood pressure after the subject had been standing for at least 2 to 4 minutes, compared to the systolic blood pressure and diastolic pressure measured in the supine position, respectively.

Orthostatic tachycardia is defined as a heart rate increase of \geq 20 beats per minute (bpm) and a heart rate of >100 bpm after the subject was standing for at least 2 to 4 minutes, compared to the heart rate measured in the supine position.

The number and percentage of subjects with orthostatic hypotension and orthostatic tachycardia will be summarized for baseline and the overall post-baseline period including follow-up visit, as well as by visit for DB period and OL period. This will be presented for systolic hypotension, for diastolic hypotension, and for both, including mean change from baseline, any orthostatic hypotension or tachycardia events that occurred at the early termination visit will be assigned to the next planned visit (as specified in Section 6.4).

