4.3. Risk-Benefit Assessment

Overall across clinical studies conducted to date, SEP-363856 has been generally well-tolerated. The majority of AEs have been mild or moderate and infrequently led to treatment discontinuation. SAEs have also been infrequent and have been reported predominantly in studies conducted in subjects with schizophrenia. A single event of hypotension experienced by a normal healthy volunteer was assessed as serious. TEAEs of hypotension and orthostatic hypotension observed to date have occurred in studies of both normal healthy volunteers and in subjects with schizophrenia, have been transient, mild or moderate in intensity and the majority did not require concomitant treatment or intervention. The PK and safety profiles observed in adult subjects from completed Phase 1 and Phase 2 clinical studies supports the evaluation of flexibly-dosed SEP-363856 at 25, 50 or 75 mg/day in adult subjects with PDP.

PD is a chronic neurodegenerative disorder that affects motor control. It is the second most common neurodegenerative disease after Alzheimer's disease and affects approximately 1 million people in the US and 7 million globally. PDP has been associated with poorer quality of life, increased morbidity and mortality, and increased caregiver burden and nursing home placement (Aarsland-2000). NuplazidTM (pimavanserin), a selective 5-HT2A inverse agonist, is the first treatment approved for PDP by the US FDA. SEP-363856 has a novel mechanism of action not related to direct antagonism of the D₂ or 5-HT_{2A} receptors and may benefit patients with PDP.

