16. SAFETY OUTCOMES

All outputs for safety outcomes will be based on the safety population.

There will be no statistical comparisons between the treatment groups for safety data, unless otherwise specified in the relevant sections. Descriptive statistics will be presented for anxiolytic or hypnotic medication taken since last visit.

Document:

\

Author:

Version Number:

Final 1.0

Version Date:

24FEB2020

Template No: CS_TP_BS016 Revision 4
Effective Date: 01Apr2016

Reference: CS_WI_BS005

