16.3. ECG EVALUATIONS

Results from the central ECG (Electrocardiogram) will be included in the reporting of this study.

The following ECG parameters will be reported for this study:

- PR Interval (msec)
- RR Interval (msec)
- QRS Interval (msec)
- QT Interval (msec)
- QTcF Interval (msec) [derived]
- QTcB Interval (msec) [derived]
- Heart rate (HR) (beats/min)
- ECG findings
- Overall assessment of ECG (investigator's judgment):
 - Normal
 - Abnormal, clinically Significant [CS]
 - Abnormal, not clinically significant [NCS]

The following summaries will be provided for ECG data for DB period and OL period:

- By visit summary of observed values and changes from baseline (for quantitative measurements)

Document:

\

Author:

Version Number:
Version Date:Final 1.0
24FEB2020Template No: CS_TP_BS016 Revision 4
Effective Date: 01Apr2016

Reference: CS_WI_BS005

- By visit summary of ECG overall assessment results
- Shift in ECG overall assessments from baseline to Week 6 for DB period, and from baseline to post-OL baseline visits for OL period

Number and percentage of subjects with QTc levels in each of the QTc categories will be presented. For the OL extension period, both the DB baseline and the OL baseline will be used in the calculation of change from baseline values, and for shift from baseline.

The number and percentage of subjects with QTc values in the following categories will be identified for DB period and OL period. The same criteria apply to both QTcF and QTcB.

- > 450 msec at any post-baseline time point (including unscheduled visits) not present at baseline
- > 480 msec at any post-baseline time point (including unscheduled visits) not present at baseline
- > 500 msec at any post-baseline time point (including unscheduled visits) not present at baseline
- ≥ 30 msec and <60 msec increase from baseline for at least one post-baseline measurement (including unscheduled visits)
- ≥ 60 msec increase from baseline for at least one post-baseline measurement (including unscheduled visits)

All ECG parameters, overall interpretation, and findings will be provided in data listings.

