16.4. VITAL SIGNS

The following vital signs measurements will be reported for this study:

- Supine Systolic Blood Pressure (mmHg)
- Standing Systolic Blood Pressure (mmHg)
- Supine Diastolic Blood Pressure (mmHg)
- Standing Diastolic Blood Pressure (mmHg)
- Supine Pulse Rate (beats/min)
- Standing Pulse Rate (beats/min)
- Respiratory Rate (breaths/min)
- Temperature (C)
- Weight (kg)
- BMI (kg/m²)

The following summaries will be provided for vital signs data:

- Observed value and change from baseline by visit including the follow-up visit for DB period and OL period. For the OL extension period, both the DB baseline and the OL baseline will be used in the calculation of change from baseline values
- BMI Categories will be described by visit for DB period and OL period.

All vital signs data will be provided in a data listing for DB period and OL period, including flagging of PCS results.

PCS Criteria

Parameter Name	PCS Low	PCS High
----------------	---------	----------

Document:

\

Author:

Version Number:

Final 1.0

Version Date:

24FEB2020

Template No: CS_TP_BS016 Revision 4
Effective Date: 01Apr2016

Reference: CS_WI_BS005

Systolic Blood Pressure (mmHg) Standing and Supine	Value \leq 90 and \geq 20 decrease from baseline	Value \geq 180 and \geq 20 increase from baseline
Diastolic Blood Pressure (mmHg) Standing and Supine	Value \leq 50 and \geq 15 decrease from baseline	Value \geq 105 and \geq 15 increase from baseline
Pulse Rate (beats/min) Standing and Supine	Value \leq 50 and \geq 15 decrease from baseline	Value \geq 120 and \geq 15 increase from baseline
Weight (kg)	\geq 7% decrease from baseline	\geq 7% increase from baseline
Temperature (°C)	Value \leq 35°C	Value \geq 38.3°C
Respiratory (breaths/min)	Value \leq 11 and \geq 10 decrease from baseline	Value \geq 25 and \geq 10 increase from baseline

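### SAP 16.4.1 does not separate new orthostatic findings from those already present at baseline, so no planned table counts new cases by arm

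*SAP*

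**What the plan says.** SAP 16.4.1 defines orthostatic hypotension within one assessment: the standing reading is "compared to the systolic blood pressure and diastolic pressure measured in the supine position, respectively". Orthostatic tachycardia is defined in the same way from heart rate. The planned summary is: "The number and percentage of subjects with orthostatic hypotension and orthostatic tachycardia will be summarized for baseline and the overall post-baseline period", with the follow-up visit included, and by visit, with mean change from baseline added. The section puts no baseline condition on the post-baseline count, plans no shift table, and does not say whether the double-blind (DB) or open-label (OL) baseline applies in the OL period.

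Other safety sections of the same SAP do more:

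- SAP 16.3 counts QTc outliers as "> 450 msec at any post-baseline time point (including unscheduled visits) not present at baseline", with the same rule at 480 and 500 msec, and plans "Shift in ECG overall assessments from baseline to Week 6 for DB period".
- SAP 16.2 plans laboratory shift tables, and 16.6.1 plans shifts in suicidal ideation score.
- SAP 16.4 makes the potentially clinically significant (PCS) limits for blood pressure relative to baseline.
- SAP 16.3 and 16.4 state that both baselines are used for change in the OL period.

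**The concern.** Protocol 4.3 names this harm: "TEAEs of hypotension and orthostatic hypotension observed to date have occurred in studies of both normal healthy volunteers and in subjects with schizophrenia". It describes these events as transient and mild or moderate, and reports one hypotension event in a healthy volunteer as serious. Protocol 7.1 requires orthostatic readings 1 and 2 hours after the first dose and after each up-titration. Protocol 7.3 says that the drug had not been given in Parkinson's disease and that no data existed at age 65 or over. No eligibility criterion names orthostatic hypotension, so subjects who already have it can enrol.

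The first question a reader will ask is how many subjects developed the finding after starting treatment, by arm. The planned rows give how many had it before and how many had it at some later reading. The overlap between the two groups is not shown. With arms this small, a few subjects with a baseline finding can shape how the table reads.

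**Working it through.** **Inputs.** Arms of about 24 and 12 (SAP 3.4). Four scheduled post-baseline DB visits, Visits 4 to 7 (Protocol Table 2), plus the post-dose readings. The documents give no orthostatic rate and no safety power.

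**The plan's own figure.** The only design calculation is power for SAPS-PD. A two-sample t-test with 34 degrees of freedom and noncentrality d × √(24 × 12 / 36) gives 59.4%, 48.6%, 37.8% and 28.0% for d = 0.8, 0.7, 0.6 and 0.5. The stated values are 59%, 48%, 37% and 27%. The arm sizes are confirmed; nothing follows for orthostatic findings.

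**What the planned count contains.** Let b be baseline prevalence, r the share of baseline cases seen again, and p the new-onset rate. Then

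any post-baseline rate = b × r + (1 − b) × p.

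All three quantities are assumptions. Take p = 30% on SEP-363856 and 5% on placebo. Among subjects free of the finding at baseline, the difference is 25 points at every b (ratio 6.0).

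*Case 1: every baseline case recurs in both arms (r = 1).*

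| b | SEP-363856 | Placebo | Difference | Ratio |
|---|---|---|---|---|
| 20% | 0.20 + 0.80 × 0.30 = 44% | 0.20 + 0.80 × 0.05 = 24% | 20 points | 1.8 |
| 40% | 0.40 + 0.60 × 0.30 = 58% | 0.40 + 0.60 × 0.05 = 43% | 15 points | 1.3 |
| 50% | 0.50 + 0.50 × 0.30 = 65% | 0.50 + 0.50 × 0.05 = 52.5% | 12.5 points | 1.2 |

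*Case 2: recurrence of 90% on SEP-363856 and 60% on placebo.*

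| b | SEP-363856 | Placebo | Difference |
|---|---|---|---|
| 20% | 0.18 + 0.24 = 42% | 0.12 + 0.04 = 16% | 26 points |
| 40% | 0.36 + 0.18 = 54% | 0.24 + 0.03 = 27% | 27 points |
| 50% | 0.45 + 0.15 = 60% | 0.30 + 0.025 = 32.5% | 27.5 points |

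Case 1 dilutes the difference; Case 2 does not.

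**Chance of a misleading table.** Baseline cases were simulated as binomial (24, b) and (12, b), and new onset as binomial among the rest. Results are for b = 20%, 40% and 50%.

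| Quantity | Planned count | New-onset count |
|---|---|---|
| SEP-363856 rate no higher than placebo, Case 1 | 13%, 23%, 28% | 3%, 6%, 8% |
| Same, Case 2 | 5.6%, 6.7%, 6.9% | 3.0%, 5.7%, 8.0% |
| No drug effect (5% new onset in both arms, r = 1), yet SEP-363856 looks at least 20 points worse | 10%, 14%, 15% | 1%, 2%, 3% |

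The chance of a baseline imbalance of at least 20 points in either direction is 18%, 28% and 29%.

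**Baseline row against post-baseline row.** The baseline percentage rests on one value per subject and the overall post-baseline percentage on several. If each visit carried an assumed, independent 10% chance of the finding, four visits would give 1 − 0.9⁴ = 34% with no drug effect.

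**Denominator.** Counting new cases over all subjects gives, at b = 20%, 0.80 × 0.30 = 24% against 0.80 × 0.05 = 4%. That restores the ratio of 6.0, but the difference is 20 points, the same as in Case 1. Only the at-risk denominator recovers both.

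**The case against.** Several points on the other side stand.

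- A reader might infer that pre-existing cases are presented as events on drug. The SAP does not do that. This is a vital-sign table labelled post-baseline, and it includes the follow-up visit about 7 days after the last dose. Adverse events are counted separately by onset (SAP 16.1), so orthostatic hypotension reported as an adverse event does get a treatment-emergent count.
- A reader might infer that the arm difference must shrink. Case 2 shows otherwise, and at b = 50% the planned count misleads slightly less often there than the new-onset count. The placebo rate matters too: with new onset of 30% versus 10%, the new-onset count itself shows no excess in 9%, 13% and 15.5% of trials.
- A reader might infer that the SAP takes more care over QTc, as a risk the protocol does not cite, than over one it names. The available text of the safety summary in Protocol 4.2 breaks off, so nothing can be said about what the protocol cites on QTc. The contrast shows only that the SAP already has a suitable rule.
- Baseline counts appear in the same summary, so an imbalance is visible. Mean changes are planned, and "All vital signs data will be provided in a data listing for DB period and OL period, including flagging of PCS results". With about 36 subjects, a diligent reader could reconstruct new cases.
- No inference is affected: "There will be no statistical comparisons between the treatment groups for safety data, unless otherwise specified in the relevant sections", and 16.4.1 specifies none.
- SAP 8 leaves table content to templates not seen here, which may hold a split.

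What remains is that none of this is a prespecified new-onset count by arm. Mean change identifies no one, and listings are data rather than a result. Under Protocol 12.2 an abnormal objective finding becomes an adverse event only when judged clinically significant, so the adverse event tables depend on investigator reporting and cannot replace a count from readings.

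**Conclusion.** The concern holds as a gap in description. As written, SAP 16.4.1 cannot show how many subjects newly met the orthostatic criteria, for a harm that the protocol names, and chance baseline imbalance carries into the arm contrast. The contrast can be diluted or inflated. Under the assumptions above, the planned difference lies between 12.5 and 27.5 points where the at-risk difference is 25. These figures rest on assumed prevalence, recurrence and new-onset rates and show only that the direction is not fixed. The effect is on how a descriptive table is read, not on any test, so this is a worthwhile improvement rather than a flaw in the trial's inference.

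**What to change.** In SAP 16.4.1 add, by arm and separately for hypotension and tachycardia:

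1. n/N (%) of subjects who meet the criterion at any post-baseline reading, including post-dose and unscheduled readings, where N is the subjects who did not meet it at baseline.
2. A shift table of baseline status by any post-baseline status, so that subjects with a baseline finding stay visible.
3. The reference used: the DB baseline for the DB period, and both the DB and OL baselines for the OL period, in line with SAP 16.3 and 16.4. The choice matters because the OL baseline is Visit 7 (SAP 6.2), after six weeks on drug for one arm.

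Keep the current table.

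The cost is SAP wording and a small amount of extra output from readings already collected; no clinical procedure changes. The new-onset denominators are smaller, about 12 versus 6 if half the subjects have the finding at baseline. A yes/no shift table will not show worsening in those who already had it; the blood pressure changes in SAP 16.4 remain the source for that.

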16.5. PHYSICAL AND NEUROLOGICAL EXAMINATION

Physical and neurological examination will be provided in a data listing including follow-up data. Subjects on-period information will be added to the neurological examination listing.

Document:	\
Author:	Version Number: Version Date:
	Final 1.0 24FEB2020

Template No: CS_TP_BS016 Revision 4
Effective Date: 01Apr2016

Reference: CS_WI_BS005

16.6. OTHER SAFETY ASSESSMENTS

16.6.1. COLUMBIA SUICIDE SEVERITY RATING SCALE (C-SSRS)

The C-SSRS is a tool designed to systematically assess and track suicidal behavior and suicidal ideation for life time, one month (30 days) prior to the screening visit, and throughout the study. The strength of this suicide classification system is in its ability to comprehensively identify suicidal events while limiting the over-identification of suicidal behavior. The C-SSRS Baseline/Screening Version is used at the screening visit and the C-SSRS Since Last Visit Version is used from Visit 2 (lead-in) onward. Subjects with Type 4 (active suicidal ideation with some intent to act, without specific plan) or Type 5 (active suicidal ideation with specific plan and intent) suicidal ideation during the study will be discontinued from the study and referred to a mental health professional.

C-SSRS includes four sections: Suicidal Ideation, Intensity of Ideation, Suicidal Behavior, and Answer for Actual Suicide Attempts.

The following outcomes are C-SSRS categories and have binary responses (yes/no). The categories are re-ordered from the scale to facilitate the definitions of the C-SSRS endpoints, and to provide clarity in the presentation of the results.

Suicidal ideation is measured by 5 categories, representing 5 subtypes of suicidal ideation with increasing severity:

- o Category 1: Wish to be Dead
- o Category 2: Non-specific Active Suicidal Thoughts
- o Category 3: Active Suicidal Ideation with Any Methods (Not Plan) without Intent to Act
- o Category 4: Active Suicidal Ideation with Some Intent to Act, without Specific Plan
- o Category 5: Active Suicidal Ideation with Specific Plan and Intent

Suicidal behavior is measured by 5 categories, representing 5 subtypes of suicidal behavior:

- o Category 6: Preparatory Acts or Behavior
- o Category 7: Aborted Attempt
- o Category 8: Interrupted Attempt
- o Category 9: Actual Attempt (non-fatal)
- o Category 10: Completed Suicide

The 10 categories above are not mutually exclusive. Subjects will be counted in each category for which they have an event.

Self-injurious behavior without suicidal intent is a non-suicide-related C-SSRS outcome, and also has a binary response (yes/no).

For the purpose of C-SSRS analysis, “baseline” and “post-baseline” for DB period are defined as follows.

Time point	Study Visit	C-SSRS Version	Derivation Rule
Baseline	Screening/Visit 1	Baseline/Screening – Past 1 Month	Most severe outcome

17. PHARMACOKINETIC AND PHARMACOGENOMIC ANALYSIS

17.1. POPULATION PHARMACOKINETIC ANALYSIS

All plasma concentrations of SEP-363856 and SEP-363854 will be presented in data listings.

Population pharmacokinetic (PK) analysis will be performed using plasma SEP-363856 concentrations. The results will be reported separately.

17.2. PHARMACODYNAMIC ANALYSIS

The relationship between SAPS-PD total score and plasma SEP-363856 exposure using population PK/pharmacodynamics (PD) methods will be explored. The results will be reported separately.

Document:

\

Author:

Version Number:
Version Date:

Final 1.0
24FEB2020

Template No: CS_TP_BS016 Revision 4
Effective Date: 01Apr2016

Reference: CS_WI_BS005

17.3. PHARMACOGENOMIC ANALYSIS

The impact of cytochrome (CYP) P450 CYP2D6 metabolizer status on plasma SEP-363856 exposure will be explored. The results will be reported separately.

18. DATA NOT SUMMARIZED OR PRESENTED

The data not summarized or presented are:

- Any data other than disposition, demographics and adverse events that are collected on screen failures and on enrolled subjects at the previously failed screenings.

These data will not be summarized or presented, but will be available in the clinical study database, SDTM and/or ADaM datasets.

19. CHANGES IN THE ANALYSIS SPECIFIED IN THE STATISTICAL ANALYSIS PLAN

Any changes or deviations during the analysis and reporting process from the statistical analysis plan designed will be described and justified in the final report.

APPENDIX 1. PROGRAMMING CONVENTIONS FOR OUTPUTS

OUTPUT CONVENTIONS

Where applicable, the Appendix_Compilation_Working_Guidelines_Final 07May2014 .pdf document – provided by Sunovion – will be followed.

In addition, the following output conventions are to be followed:

- o The first row in the body of the table or listing should be blank
- o The left-hand column should start in column 1. No indenting or centering of the output should occur.
- o Rounding should be done with the SAS function ROUND.
- o Numbers in tables should be rounded, not truncated.
- o Alphanumeric output should be left aligned.
- o Numbers should be decimal point aligned.
- o Whole numbers should be right aligned.
- o Text values should be left aligned.
- o The first letter of a text entry should be capitalized.
- o The width of the entire output should match the linesize (134)
- Univariate Statistics:
 - o If the raw data has N decimal places, then the summary statistics should have the following decimal places:
 - o Minimum and maximum: N
 - o Mean, median, Q1, and Q3: N + 1
 - o SD: N + 2
- Frequencies and percentages (n and %):
 - o Percent values should be reported inside parentheses, with one space between the count (n) and the left parenthesis of the percentage. Parentheses should be justified to accept a maximum of 100.0 as a value and padded with blank space if the percent is less than 100.0.
 - o Percentages will be reported to one decimal place, except cases where percent <100.0% but >99.9% will be presented as '>99.9%' (e.g., 99.99% is presented as >99.9%); and cases where percent < 0.1% will be presented as '<0.1%' (e.g., 0.08% is presented as <0.1%). Rounding will be applied after the <0.1% and >99.9% rule.
 - o Where counts are zero, no percentage should appear in the output.
- Confidence Intervals:
 - o Confidence intervals and estimates are presented to one place more than the raw data, and standard errors to two places more than the raw data.
 - o Confidence intervals should be justified so that parentheses displayed on consecutive lines of a table “line up”.
 - o Boundary values of confidence intervals should be separated by a comma.

Document:

\

Author:

Version Number:

Final 1.0

Version Date:

24FEB2020

Template No: CS_TP_BS016 Revision 4
Effective Date: 01Apr2016

Reference: CS_WI_BS005

- o Boundary values should be padded as necessary to accept negative values and to allow alignment of the decimal place.
- P-values:
 - o P-values should be reported to three decimal places, except values <1.000 but >0.999 will be presented as '>0.999' (e.g., 0.9998 is presented as >0.999); and values <0.001 will be presented as '<0.001' (e.g., 0.0009 is presented as <0.001). Rounding will be applied after the <0.001 and >0.999 rule.
- Ratios:
 - o Ratios should be reported to one more decimal place than the raw data.
- Spacing:
 - o There must be a minimum of 1 blank space between columns (preferably 2).
- Missing values:
 - o A "0" should be used to indicate a zero frequency.
 - o A blank will be used to indicate missing data in an end-of-text table or subject listing.
- Figures:
 - o Figures should be provided in RTF files using the SAS Output Delivery System (ODS), as Computer Graphics Metafile (CGM) formatted graphical output generated by SAS.
 - o The CGM file itself should contain the title or footer.
 - o The image should be clear and of high quality when viewed in the Word document, and when printed.
 - o In general, boxes around the figures should be used.
- Footers should be defined as follows:
 - o A continuous line of underscores ('_') will follow the body of the table or listing prior to any footnotes at the bottom of the page.
 - o Table footnotes should be defined using compute statements in the proc report, and should appear directly after the body of the table.
 - o If text wraps across more than one line (for a note), the first letter for all lines of text after the first one will be indented to align beneath the first letter of the text in the first line.

DATES & TIMES

Depending on data available, dates and times will take the form yyyy-mm-ddThh:mm:ss.

Document:

\

Author:

Version Number:

Final 1.0

Version Date:

24FEB2020

Template No: CS_TP_BS016 Revision 4
Effective Date: 01Apr2016

Reference: CS_WI_BS005

SPELLING FORMAT

English US.

PRESENTATION OF TREATMENT GROUPS

For outputs, treatment groups will be represented as follows and in that order:

Treatment Group	For Tables, Graphs and Listings in DB period	For Tables, Graphs and Listings in OL period
Placebo	Placebo	
SEP-363856 (25, 50 or 75 mg/day)	SEP-363856	SEP-363856

LISTINGS

All listings will be ordered by the following (unless otherwise indicated in the template):

- Actual treatment received, displaying SEP-363856 first and then placebo,
- Subject ID,
- Date/Time (where applicable) - listings of adverse events, concomitant medications, medical histories etc. should be sorted in chronological order, with earliest adverse event, medication or history coming first,
- For listings where non-randomized subjects are included, these will appear in a category after the randomized treatment groups labelled 'Not Randomized'.

Document:

\

Author:

Version Number:

Final 1.0

Version Date:

24FEB2020

Template No: CS_TP_BS016 Revision 4
Effective Date: 01Apr2016

Reference: CS_WI_BS005

